# STUDY PROTOCOL

## Objectives

To determine if the incidence of postoperative pillar pain is lower for either of the two surgical techniques being studied after 3 weeks and 6 months of follow-up

Secondary, to check if the post-surgical grip strength, pinch strength and Borton Carpal Tunnel Questionnaire (BCTQ) score are better for either of the two surgical techniques

## Design

Randomised clinical trial.

## Methods

### Study variables

- Signs of compression of the median nerve: pain and paresthesias in the first three fingers and radial edge of the fourth finger, nocturnal paresthesias, thenar muscle atrophy, loss of opposition of the thumb. Durkan, Phalen, Tinel signs.
- Pillar pain*: pain/sensation of allodynia in the area of the thenar and/or hypothenar eminence, hyperalgesia in the scar, pain when supporting the heel of the hand, dysesthesia at rest.
- Questionnaire: BCTQ (Boston Carpal Tunnel Syndrome Questionnaire).
- Grip strength and pinch strength with specific dynamometers

### Inclusion criteria

- 1) Age > 18 years
- 2) Moderate-severe carpal tunnel syndrome
- 3) Symptoms that hinder the patient's daily activities
- 4) Have performed a correct conservative treatment without success

### Exclusion criteria

- 1) Previous carpal tunnel syndrome surgery
- 2) Traumatic or congenital sequelae of the hand
- 3) Unable to understand the process and the tests to be performed

### Design

The follow-up process was carried out in three visits (3 weeks and 6 months after surgery).

In the **pre-surgery visit**, we carried out: patient screening and recruitment, patient information and obtaining informed consent process, application of the **inclusion and exclusion criteria**, medical history and physical examination of the hand to reach the **clinical and exploratory diagnosis of carpal tunnel syndrome**, obtaining baseline values from the **BCTQ questionnaire**, obtaining baseline **grip** and **pinch strength** values. After that, patients were **randomly assigned** to one of two treatment groups. Once included in each study group, the specific **surgical operation** was carried out. Finally, in the **post-surgery visits (3 weeks and 6 months post-surgery)**, we evaluated: clinical and

examination of the median nerve compression clinic, presence or not of **pillar pain**, post-operative BCTQ values and grip and pinch strengths.

## STATISTICAL ANALYSIS PLAN (SAP)

To carry out the sample homogeneity study, the statistical Student t-tests for the quantitative variables and chi-square for the qualitative variables were used. For the analysis of the qualitative variables the chi-square statistical test was used. Mixed ANOVA was used using the patient as a random effect and using the visit and surgical technique as a fixed effect to analyse the absolute change in grip and pinch strength and the BCTQ score after 3 weeks and 6 months after surgery.

As for the data analysis, two new variables were created for the quantitative variables: the absolute change in grip strength, in pinch strength and in the BCTQ score and the relative change therein, performed by an absolute and percentage calculation (respectively) of the difference between values after 3 weeks from baseline and values after 6 months from baseline; i.e., comparing each patient with themselves calculating the variation in these variables throughout the follow-up.

Finally, the Student's t-test was used to study the absolute and relative change in the grip and pinch strength and BCTQ values.

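### Pillar pain, the first-listed objective, is planned for a chi-square test only, with no between-technique difference or confidence interval, so a non-significant p-value alone would not show what has been ruled out

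*Combined protocol and SAP*

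**What the plan says.** The Objectives section opens with pillar pain: "To determine if the incidence of postoperative pillar pain is lower for either of the two surgical techniques being studied". The comparison is set for two time points, 3 weeks and 6 months. The other outcomes follow under a different label: "Secondary, to check if the post-surgical grip strength, pinch strength" and the BCTQ score. The word primary is not used, but the order and the label make pillar pain the lead outcome.

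The Design section under Methods makes the outcome binary, since the post-surgery visits record "presence or not of pillar pain". Patients are randomised "to one of two treatment groups"; no allocation ratio is given.

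In the SAP, the sentence that reaches a binary outcome is "For the analysis of the qualitative variables the chi-square statistical test was used". The other methods are confined to the quantitative outcomes. The mixed ANOVA is there "to analyse the absolute change in grip and pinch strength and the BCTQ score after 3 weeks and 6 months after surgery". The absolute and relative changes are likewise restricted: "two new variables were created for the quantitative variables". They are changes from each patient's own baseline, and the closing t-tests are applied to them.

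Neither the protocol nor the SAP names a risk difference, risk ratio, odds ratio or confidence interval for any outcome. Neither states a sample size, power, significance level, expected pillar-pain rate or target difference.

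**The concern.** The objective is about direction and, implicitly, amount: is pillar pain less frequent with one technique, and by how much? A chi-square statistic has no sign, and its p-value mixes the size of the difference with the number of patients. Given only that p-value, a reader of a non-significant result could not tell whether the two techniques are close or whether the trial was too small to show a gap that matters. Usually the design assumptions help, because a trial powered for a named difference gives a null result some meaning. Here none are stated. The same gap affects a significant result: the p-value does not show how small the benefit might be. At stake is how the trial's leading result is read, and whether the effect measure is chosen before or after the counts are seen.

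**Working it through.** **Inputs.** The documents give no figure to reproduce. All counts, rates and arm sizes below are assumptions chosen for illustration, with equal arms of n patients and a two-sided 5% level.

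**Formulas.** With p1 and p2 the two proportions, d = p1 - p2, and p̄ their mean:
- Uncorrected chi-square: d² / [p̄(1 - p̄) × 2/n], on 1 degree of freedom.
- Newcombe 95% interval, from the Wilson limits (l1, u1) and (l2, u2) of each proportion: lower = d - √[(p1 - l1)² + (u2 - p2)²]; upper = d + √[(u1 - p1)² + (p2 - l2)²].

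**Step 1. Nearly the same p-value, very different information.**

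*9/30 against 6/30.* d = 10.0 points, p̄ = 0.25. Chi-square = 0.01 / (0.1875 × 0.06667) = 0.80, p = 0.37. Wilson limits in percent: 16.66 to 47.88 and 9.51 to 37.31.
- Lower = 10.0 - √(13.34² + 17.31²) = 10.0 - 21.85, about -12.
- Upper = 10.0 + √(17.88² + 10.49²) = 10.0 + 20.73, about 31.

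*150/500 against 137/500.* d = 2.6 points, p̄ = 0.287. Chi-square = 0.000676 / (0.204631 × 0.004) = 0.826, p = 0.36. Wilson limits in percent: 26.15 to 34.16 and 23.67 to 31.47.
- Lower = 2.6 - √(3.85² + 4.07²) = 2.6 - 5.60 = -3.0.
- Upper = 2.6 + √(4.16² + 3.73²) = 2.6 + 5.59 = 8.2.

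The intervals are about 43 and 11 points wide. Reported by p-value alone, the two results look alike. The second excludes a 10-point difference in either direction; the first excludes neither.

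**Step 2. Identical observed rates.** With 20% in both arms, p = 1.00 at every size. The Newcombe interval is ±20 points at 30 per arm, ±16 at 50 and ±11 at 100. All three still include a 10-point difference, which is a halving from 20%.

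**Step 3. An observed halving.** 10/50 against 5/50 gives p = 0.16 and a difference of 10 points, with a 95% interval of -4 to 24.

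**Step 4. Power to detect a halving** (normal approximation, assumed control rates):

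| n per arm | 20% to 10% | 30% to 15% | 40% to 20% |
|---|---|---|---|
| 30 | 19% | 28% | 39% |
| 50 | 29% | 43% | 59% |
| 100 | 51% | 72% | 88% |

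For 80% power, the numbers per arm would be 199, 121 and 82. Whether a null result is informative therefore depends on quantities that the plan does not give.

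**Step 5. Near the threshold.** 11/50 against 4/50: d = 14 points, p̄ = 0.15, chi-square = 0.0196 / (0.1275 × 0.04) = 3.843, p = 0.0499 (0.093 with continuity correction). Wilson limits in percent: 12.75 to 35.24 and 3.15 to 18.84.
- Lower = 14 - √(9.25² + 10.84²) = 14 - 14.25, about -0.2.
- Upper = 14 + √(13.24² + 4.85²) = 14 + 14.10 = 28.1.

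The uncorrected test is just significant while the Newcombe interval just includes zero. A plan that uses both must say which one governs.

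**The case against.** The strongest reply is that nothing is lost. A chi-square test on a 2×2 table is valid, and the direction, the difference and its interval all follow from the same four counts. The SAP names a test; it does not say that only a p-value will be reported, and it nowhere says that absence of a difference will be concluded from a null result. On this view the gap is an incomplete reporting specification.

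Much of this stands. A reader might infer that the trial could not answer its own question, or that chi-square is the wrong test. The documents support neither: the needed data are collected in randomised groups, and the interval can be computed if counts per arm are reported. What remains is that the plan does not commit to reporting those counts, and it leaves the effect measure and interval method open.

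It is also fair to say that an interval displays imprecision without curing it. The missing sample-size rationale is a separate gap; it matters here because it removes the other means of interpreting a null result.

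The chi-square sentence does not name pillar pain. But pillar pain is the evident qualitative outcome, and if the sentence did not cover it, the lead outcome would have no stated analysis at all.

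The unstated continuity correction is minor. It changes the verdict in Step 5, but that table was chosen to sit at the threshold.

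**Conclusion.** The point holds as a shortfall in what is planned for the lead outcome. It does not show that the test is invalid. The text directly supports two findings: chi-square is the only method that reaches pillar pain, and no effect estimate or interval is planned. The consequence is one of interpretation: a p-value near 0.36 is compatible with an interval 43 points wide or one 11 points wide, and the plan offers nothing else to tell them apart. Those widths rest on assumed counts and say nothing about the trial's actual precision. Treating pillar pain as the lead outcome is an inference from the order of the objectives and the label on the others. The change should be made because it is specific and cheap.

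**What to change.** In the SAP, replace the chi-square sentence, as it applies to pillar pain, with text such as:

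> At 3 weeks and at 6 months, report the number and proportion with pillar pain per randomised technique and the risk difference with a Newcombe 95% confidence interval. Conclusions are based on the interval; the chi-square test without continuity correction is supportive, and if the two disagree near the threshold the interval governs. Absence of a difference will not be concluded from p>0.05; the interval states which differences are excluded.

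This also settles the continuity correction.

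The cost is wording and a short calculation, with no new patients or measurements. The downside is that a null or borderline result will look less conclusive than a bare statement of non-significance. The Design section and the SAP are written in the past tense, so the analysis may already have been done. If so, the interval should still be reported, and disclosed as an addition made after the plan was written. The new text covers both visits without ranking them; it does not settle which time point leads.

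### Absolute and percentage change are both t-tested for grip, pinch and BCTQ with neither named as deciding, so each secondary outcome has two verdicts that can conflict

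*Combined protocol and SAP*

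**What the plan says.** The SAP derives two variables for each quantitative outcome, "performed by an absolute and percentage calculation (respectively) of the difference between values after 3 weeks from baseline" and likewise for 6 months. Its last sentence then states that "the Student's t-test was used to study the absolute and relative change in the grip and pinch strength and BCTQ values".

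The same section also specifies a model: "Mixed ANOVA was used using the patient as a random effect and using the visit and surgical technique as a fixed effect", applied "to analyse the absolute change in grip and pinch strength and the BCTQ score after 3 weeks and 6 months after surgery". That model uses absolute change only. Percentage change appears in the t-tests and nowhere else.

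The Objectives place these outcomes second to pillar pain: "Secondary, to check if the post-surgical grip strength, pinch strength and Borton Carpal Tunnel Questionnaire (BCTQ) score are better".

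The SAP gives no ranking of the two scales, no rule for conflicting results, and no rule for a zero baseline.

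**The concern.** Absolute and percentage change are two readings of the same data. They need not agree, because percentage change divides each patient's gain by that patient's own pre-surgery value. If both are tested and neither leads, one technique can be called better on whichever scale favours it, and the reader cannot tell whether that scale was chosen beforehand.

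Percentage change has its own weaknesses for the dynamometer measures. Its divisor is the patient's pre-surgery reading, so measurement error counts heavily when that reading is low. It treats gains and losses unequally, and it has no value when the baseline is zero. Entry requires "Moderate-severe carpal tunnel syndrome", and the Study variables include "thenar muscle atrophy, loss of opposition of the thumb", so low readings are conceivable, particularly for pinch.

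At stake are the secondary claims about strength and BCTQ.

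**Working it through.** **Inputs.** From the SAP: three outcomes, two post-surgery visits, two scales. That gives 3 × 2 × 2 = 12 t-tests, in 6 pairs. The documents contain no planned figure to reproduce: sample size, alpha, SD, effect size and baseline values are all unstated. Everything numerical below is therefore assumed. I also read the t-tests as comparing the two techniques, as the Objectives imply; the SAP does not say so explicitly.

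**Step 1: how the scales part company.** Percentage change = 100 × (follow-up − baseline) / baseline. The same +3 kg gain gives:

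| Assumed baseline | Percentage change | If baseline is misread by 1 kg either way |
|---|---|---|
| 2 kg | 150% | 67% to 400% |
| 5 kg | 60% | 33% to 100% |
| 20 kg | 15% | 9.5% to 21% |
| 30 kg | 10% | 6.5% to 14% |

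Suppose every patient gains 3 kg. Two patients starting at 2 and 20 kg average (150 + 15)/2 = 82.5%. Two starting at 20 and 30 kg average (15 + 10)/2 = 12.5%. The absolute gains are identical, yet the percentages differ by 70 points, purely through baseline.

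On asymmetry: one patient who doubles (+100%) and one who halves (−50%) average +25%. If their values were 2 to 4 kg and 4 to 2 kg, the mean absolute change is zero.

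**Step 2: two verdicts with no true difference.** Two-sample t-tests at two-sided 0.05 on both scales were simulated with 60 per arm and a baseline-to-follow-up correlation of 0.6 or 0.8, over several baseline distributions. Rejection by at least one test was about 5–8% per outcome and visit. Two independent tests would give 1 − 0.95² = 9.75%. In the runs with a lognormal baseline and normal noise, each test alone stayed at about 4–5.5%.

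**Step 3: two verdicts with a true difference.** The shift is 0.5 SD of the change, 60 per arm. As a check on absolute change, the noncentrality is 0.5 × √(60/2) = 2.74; against a critical value of 1.98, power is about Φ(0.76) = 78%, close to the simulated values.

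| Assumed distribution | Baseline CV | Power, absolute | Power, percentage | Tests disagree |
|---|---|---|---|---|
| Normal | 0.2 | 77–78% | 71–73% | 7–9% |
| Normal, baseline floored at 5% of the mean | 0.3 / 0.4 / 0.5 | 77–78% | 54–61% / 31–38% / 22–27% | about 19–56% |
| Normal, floored at 20% of the mean | 0.3 / 0.4 / 0.5 | about 77–78% | 62–64% / 53–57% / 51–52% | 16–31% |
| Lognormal at both times | 0.2 to 0.5 | 74–77% | 77–88% | 5–16% |

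A fourth set-up used a lognormal baseline, follow-up linear in baseline with normal noise, CV 0.2 to 0.8, and a shift of 0.5 *baseline* SD. That shift equals 0.5/√(2(1 − 0.6)) = 0.56 SD of the change at correlation 0.6, and 0.79 at 0.8. At 60 per arm, absolute power was 85–99%, percentage power 63–98.5%, and disagreement 0.7–26%.

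**Reading the results.** Disagreement occurs in every set-up. The ordering of the two powers does not hold across them: percentage change is weaker in the normal models and the mixed model, and stronger when both readings are lognormal.

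**The case against.** The best defence is that the plan already leans towards absolute change. The only model combining patient, visit and technique is run on that scale, while percentage change gets a t-test alone. That is fair, but a lean is not a stated hierarchy: the closing sentence of the SAP puts the two scales on equal terms.

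A second defence is that the consequence is limited. These are secondary outcomes, and an either-test error rate of 5–8% is a modest excess over 5%. That stands, and it limits how much weight the point carries.

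Several stronger readings are tempting, and the documents do not support them:

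- *The trial enrols very weak hands.* Entry sets a disease grade but no strength threshold, and no baseline strength figure is given. Atrophy and loss of opposition are recorded signs, not entry conditions. Low or zero readings are plausible but not shown.
- *Percentage change loses power.* This depends on the assumed distribution. The largest losses come from normal baselines cut off at 5% of the mean, where a few patients have a divisor 20 times smaller than average. Raising the floor shrinks the loss, and lognormal values turn it into a gain.
- *BCTQ percentages are unstable too.* The low-baseline argument concerns dynamometer readings. The documents give no BCTQ scoring that would allow a near-zero divisor.
- *The percentage t-test is itself invalid.* Its own error rate was not inflated in the simulations; the excess comes from having two tests to choose from.

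**Conclusion.** The point holds as a matter of unranked duplicate testing. For grip, pinch and BCTQ, each visit yields two significance verdicts and no rule says which counts. On the assumed inputs (60 per arm, correlation 0.6 to 0.8, two-sided 0.05) the either-test false-positive rate is about 5–8% per outcome and visit. With a true difference of 0.5 SD of the change, disagreement runs at about 5–16% under lognormal values and 7–56% under normal values. The width of these ranges reflects the unknown baseline spread and shape.

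For grip and pinch there is the further arithmetic weakness of percentage change: asymmetry, instability at low baselines, and no value at zero. Its frequency in this trial cannot be judged from the documents. For BCTQ only the duplicate verdict applies. No general loss of power should be claimed, and the pillar pain comparison is untouched. This is a cheap improvement to the secondary analyses.

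**What to change.** In the SAP, state that conclusions about technique for grip, pinch and BCTQ are drawn from absolute change only, and remove percentage change from the closing t-test sentence. Absolute change is the natural choice because the mixed ANOVA already uses it, a reason that does not depend on the results. Report percentage change descriptively, as the median per arm at each visit. For grip and pinch, add the number of patients with a zero or near-zero baseline, with near-zero defined in the text.

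This settles the scale but not the method: absolute change would still be analysed by both the mixed ANOVA and a t-test, so the same sentence could usefully say which of those leads.

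The change needs wording and no new data. It has two costs. The familiar percentage figure no longer carries a p-value, and some power is given up if effects are in fact proportional to baseline or values are strongly right-skewed.
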